#### **6.4.2 Unblinding**

At the initiation of the study, each study site will be instructed on the method for breaking the blind. The unblinding method will be either a manual or electronic process.

Unblinding of the individual subject's treatment by the investigator will be limited to medical emergencies or urgent clinical situations in which knowledge of the subject's study treatment is necessary for clinical management. In such cases, investigators will use their best judgment as to whether to unblind without first attempting to contact the medical monitor to discuss and agree to the need for unblinding. If investigators deem it not necessary to unblind immediately, they will first attempt to contact the medical monitor to discuss and agree to the need for unblinding. If investigators have tried but are unable to reach the medical monitor, they will use their best judgment, based on the nature and urgency of the clinical situation, and may proceed with unblinding without having successfully reached and discussed the situation with the medical monitor.

Contact information for the medical monitor (or appropriate backup) will be provided in a separate document.

In addition, the Vertex Medical Information Call Center ( [REDACTED] ) will answer calls 24 hours a day, 7 days a week, 365 days of the year, and will triage these calls to the study medical monitor or appropriate backup.

If a subject's treatment assignment has been unblinded for a medical emergency or urgent clinical situation, the medical monitor will be notified within 24 hours of the unblinding event. The reason and the date of the unblinding will be documented clearly in the subject's study file. Information about the treatment assignment obtained from the unblinding will be maintained in a secure location with controlled access and will not be shared with the sponsor (Vertex), contract research organization (CRO), or any site personnel (other than the physician treating the subject). In addition, the investigator will consider whether the clinical event that prompted unblinding will be considered an SAE, according to the regulatory definitions or criteria for SAEs, and if so, submit an SAE report to Vertex GPS or designee, per Section 13.1.2 of the protocol.

Vertex GPS or designee will also unblind any SAE reports in compliance with regulatory reporting requirements. In addition, Vertex may, for matters relating to safety concerns, unblind individual subjects at any time.

## **7 ANALYSIS SETS**

The following analysis sets are defined: All Subjects Set, Full Analysis Set and Safety Set.

### **7.1 All Subjects Set**

The **All Subjects Set** will include all subjects who were randomized or received at least 1 dose of study drug. This analysis set will be used for all individual subject data listings and disposition summary tables, unless otherwise specified.

### **7.2 Full Analysis Set**

The **Full Analysis Set** (FAS) will be defined as all randomized subjects who carry the intended CFTR allele mutation and have received at least 1 dose of study drug in the Treatment Period. The FAS will be used to summarize subject demographics and baseline characteristics, and for all PD and efficacy analyses, unless specified otherwise. Subjects will be analyzed according to the treatment they were randomized to.

### **7.3 Safety Set**

#### **7.3.1 Parts 1 [REDACTED]**

The **Safety Set** will include all subjects who received at least 1 dose of study drug. The Safety Set will be used for all safety analyses, unless otherwise specified. Subjects will be analyzed according to the treatment they received.

For Part 1, if a subject received at least 1 dose of the higher TC treatment group in the increasing priority order: Triple placebo, TC-1A, TC-1B-low, TC-1B-high, the subject will be analyzed in the higher treatment group.

### 7.3.2 Part 2

The **Safety Set for the Run-in Period** will include all subjects who received at least 1 dose of study drug TEZ/IVA in the Run-in Period. This Safety Set will be used for individual subject data listings for the Run-in Period, unless specified otherwise.

The **Safety Set for the Treatment Period** will include all subjects who received at least 1 dose of study drug in the Treatment Period. This Safety Set will be used for all safety analyses for the Treatment Period, unless specified otherwise.

If a subject received at least 1 dose of the higher TC treatment group in the increasing priority order: placebo + TEZ/IVA, TC-2 (VX-440 + TEZ/IVA), the subject will be analyzed in the higher treatment group.

Note: The safety analysis will focus on the Safety Set for the Treatment Period only, unless otherwise specified.

## 8 STATISTICAL ANALYSIS

### 8.1 General Considerations

The analysis will be performed for each part, and presented by treatment group and overall, for the Treatment Period, unless specified otherwise. The treatment groups are defined as follows:

- Part 1: F508del/MF genotype group
  - TC-1B-high, TC-1B-low, TC-1A, and placebo, with the TEZ component in the TC-1B-low and TC-1B-high groups administered as 50 mg q12h, and that in the TC-1A group administered as 100 mg qd. More specifically, Part 1 includes cohorts 1A and 1B; Cohort 1A includes TC-1A while Cohort 1B includes TC-1B-low and TC-1B-high. The placebo group is randomized in both cohorts.
- Part 2: F508del/F508del genotype group
  - TC-2, and TEZ/IVA, with the TEZ component in the TC group administered as 50 mg q12h

The Schedule of Assessments is provided in Appendix A. The precision standards for reporting safety and efficacy variables are provided in an internal Biometrics document that specifies the programming rules including the precision for derived variables.

All individual subject data for those randomized or dosed with any amount of study drug will be presented in data listings.

**Continuous variables** will be summarized using the following descriptive summary statistics: the number of subjects (n), mean, SD, standard error (SE), median, minimum value (min), and maximum value (max). SE may not be reported for safety summary tables.

**Categorical variables** will be summarized using counts and percentages. Percentages will be presented to 1 decimal place.

**Baseline value**, unless otherwise specified, will be defined as the most recent non-missing measurement (scheduled or unscheduled) collected before the first dose of study drug on Day 1 of the Treatment Period. For ECG, baseline will be defined as the most recent non-missing measurement (the average of triplicate measurements, if the most recent non-missing measurement is obtained in triplicate), before the first dose of study drug on Day 1 of the Treatment Period.

**Absolute change** from baseline will be calculated as postbaseline value – baseline value.

**Relative change** from baseline will be calculated as (postbaseline value – baseline value)/baseline value.

**Treatment-emergent (TE) period** for Parts 1 [REDACTED] will include the time from the first dose of study drug in the Treatment Period to the Safety Follow-up (SFU) Visit, or 28 Days after the last dose of study drug for subjects who do not complete the SFU Visit.

For Part 2, the TE period will be defined separately for the Run-In Period, and the Treatment Period:

- The TE period for the Run-in Period will include the time from the first dose of study drug in the Run-in Period to: (1) the last day prior to the first dose of study drug in the Treatment Period for subjects who complete the Run-in Period and continue to the Treatment Period, or (2) the SFU Visit for subjects who do not continue to the Treatment Period and have an SFU Visit, or (3) 28 days after the last dose of study drug in the Run-in Period for subjects who do not have an SFU Visit (e.g., subjects who do not meet the criteria to enter the Treatment Period and re-enter Study 661-110).
- The TE period for the Treatment Period will include the first dose of study drug in the Treatment Period to: (1) the SFU Visit, or (2) 28 days after the last dose of study drug for subjects who do not have an SFU Visit (e.g. subjects whose Early Treatment Termination (ETT) Visit occurs 3 weeks or later following the last dose of study drug and the ETT visit replaces the SFU visit, or who leave the Treatment Period early and re-enter Study 661-110).

Note: only data collected up to the end of study for a subject will be included in analysis.

**Unscheduled visits:** Unscheduled visit measurements will be included in analysis as follows:

- In scheduled visit windows per specified visit windowing rules
- In the derivation of baseline and last on-treatment measurements
- In the derivation of maximum and minimum on-treatment values, and maximum and minimum change from baseline values for safety analyses
- In individual subject data listings as appropriate

**Visit windowing rules:** The analysis visit windows for protocol-defined visits are provided in Appendix B.

**Incomplete/missing data** will not be imputed, unless specified otherwise.

**Outliers:** No formal statistical analyses will be performed to detect or remedy the presence of statistical outliers, unless specified otherwise.

**Multiplicity:** There will be no multiplicity adjustment for performing multiple hypothesis tests, unless specified otherwise.

## **8.2 Background Characteristics**

### **8.2.1 Subject Disposition**

For the Treatment Period in Part 1, Part 2, [REDACTED], subject disposition will be summarized as described below.

The number of subjects in the following categories will be summarized by treatment group and overall, for each part:

- All Subjects Set (randomized or dosed in the Treatment Period)
- Randomized
- Full Analysis Set (FAS)
- Safety Set (for Part 2, this is the Safety Set for the Treatment Period)

The number and percentage (based on FAS) of subjects in each of the following disposition categories will be summarized by treatment group and overall:

- Completed study drug treatment
- Prematurely discontinued treatment and the reason for discontinuation (i.e., discontinued all study drugs)
- Completed study (i.e., completed Safety Follow-up Visit or completed all study drugs and re-entered Study 661-110 without Safety Follow-up per protocol)
- Prematurely discontinued the study and the reason for discontinuation

For the Run-in Period in Part 2, a separate disposition table will be provided with the following categories:

- All Subjects Set (enrolled or dosed in the Run-in Period)
- Completed treatment in the Run-in Period (i.e., completed randomization)
- Prematurely discontinued treatment during the Run-in Period and the reason for treatment discontinuation (i.e., discontinued all study drugs in the Run-in Period)
- Prematurely discontinued the study during the Run-in Period and the reason for study discontinuation

A listing will be provided by part, for subjects who discontinued treatment (including the Run-in Period in Part 2) or who discontinued study with reasons for discontinuation. A randomization listing of subjects will also be provided, by part.

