8.1.6 Early Termination of Treatment

If a subject prematurely discontinues treatment, an Early Termination of Treatment (ETT) Visit should be scheduled as soon as possible after the decision to terminate study drug treatment. Subjects who prematurely discontinue treatment will also be required to complete the Safety Follow-up Visit, approximately 28 days after their last dose of study drug.

If the ETT Visit occurs 3 weeks or later following the last dose of study drug, then the ETT Visit will replace the Safety Follow-up Visit, and a separate Safety Follow-up Visit will not be required.

If a subject withdraws from the study and also withdraws consent for disclosure of future information, no further evaluations should be performed and no additional data should be collected. Vertex may retain and continue to use any data collected before such withdrawal of consent.

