## Appendix B: Analysis Visit Windows for Safety and Efficacy Assessments

Table 11-5 Analysis Visit Windows for Safety and Efficacy Assessments			
Assessment	Visita	Target Study Dayb	Analysis Visit Window (in study days)
Safety Assessment (Part 1, Cohort 1A)			
Serum Chemistry Hematology Urinalysis Vital Signs (including Weight)	Day 1 (Baseline)	1	≤1 Pre-dose
	Day 8	8	[1, 12]
	Day 15	15	(12,22]
	Day 29	29	(22, 36]
	Day 43	43	(36, 50]
	Safety Follow-up	57	Use nominal visit
Coagulation	Day 1 (Baseline)	1	≤1 Pre-dose
	Day 15	15	[1, 22]
	Day 29	29	(22, 43]
	Safety Follow-up	57	Use nominal visit
Standard 12-Lead ECG	Day 1 (Baseline; before dosing)	1	Use nominal visit for all visits
	Day 1 (4 hours after dosing)	1	
	Day 8	8	
	Day 15 (before dosing and 4 hours after dosing)	15	
	Day 29	29	
	Day 43	43	
	Safety Follow-up	57	
Safety Assessment (Part 1, Cohort 1B)			
Serum Chemistry Hematology Urinalysis Vital Signs (including Weight)	Day 1 (Baseline)	1	≤1 Pre-dose
	Day 15	15	[1,22]
	Day 29	29	(22, 36]
	Day 43	43	(36, 50]
	Safety Follow-up	57	Use nominal visit
Coagulation	Day 1 (Baseline)	1	≤1 Pre-dose
	Day 15	15	[1,22]
	Day 29	29	(22, 43]
	Safety Follow-up	57	Use nominal visit
Standard 12-Lead ECG	Day 1 (Baseline; before dosing)	1	Use nominal visit for all visits
	Day 1 (4 hours after dosing)	1	
	Day 15 (before dosing and 4 hours after dosing)	15	
	Day 29	29	
	Day 43	43	
	Safety Follow-up	57	
Safety Assessment (Part 2)			

a Visit name is used to report data in tables, listings and figures.

b Target day time point per protocol is pre-dose, except for ECG measurements.

Table 11-5 Analysis Visit Windows for Safety and Efficacy Assessments			
Assessment	Visita	Target Study Dayb	Analysis Visit Window (in study days)
Serum Chemistry Hematology Urinalysis Vital Signs (including Weight)	Day 1 (Baseline)	1	≤1 Pre-dose
	Day 15	15	[1,22]
	Day 29	29	(22, 36]
	Day 43	43	(36, 50]
	Day 57	57	(50, 71]
	Safety Follow-up	85	Use nominal visit
Coagulation	Day 1 (Baseline)	1	≤1 Pre-dose
	Day 15	15	[1,22]
	Day 29	29	(22, 57]
	Safety Follow-up	85	Use nominal visit
Standard 12-Lead ECG	Day 1 (Baseline; before dosing)	1	Use nominal visit for all visits
	Day 1 (4 hours after dosing)	1	
	Day 15 (before dosing and 4 hours after dosing)	15	
	Day 29	29	
	Day 43	43	
	Day 57	57	
	Safety Follow-up	85	

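### SAP 8.2.1 does not count a subject as completing the study when a late ETT Visit replaces Safety Follow-up, and Table 11-5 gives that visit no Safety Follow-up row

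*SAP*

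**What the plan says.** **Protocol 8.1.6.** A subject who stops treatment early has an ETT Visit as soon as possible and then a Safety Follow-up Visit about 28 days after the last dose. There is one exception. When the gap from last dose to ETT Visit reaches 3 weeks, "then the ETT Visit will replace the Safety Follow-up Visit, and a separate Safety Follow-up Visit will not be required". Footnote c of the schedules for Cohort 1A, Cohort 1B and Part 2 repeats it. Protocol 13.1.1.3 also uses it, when setting the end of adverse event collection.

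**SAP 8.1.** For Part 2, the TE period ends 28 days after the last dose for subjects without a Safety Follow-up Visit. The examples given include "subjects whose Early Treatment Termination (ETT) Visit occurs 3 weeks or later following the last dose of study drug and the ETT visit replaces" that visit. For Part 1, the same 28-day limit applies to anyone who does not complete Safety Follow-up.

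**SAP 8.2.1.** The study-level disposition categories are "Completed study (i.e., completed Safety Follow-up Visit or completed all study drugs and re-entered Study 661-110 without Safety Follow-up per protocol" and "Prematurely discontinued the study and the reason for discontinuation".

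**SAP Appendix B, Table 11-5.** The Part 1 follow-up row reads "Safety Follow-up 57 Use nominal visit". Part 2 has the same rule with target Day 85. ECGs use the nominal visit throughout. The table has no ETT row.

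**The concern.** The protocol treats the late ETT Visit as a full substitute for Safety Follow-up. The SAP carries this into the TE period but not into the two other places where it matters.

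In the disposition table, a subject who owes no further visit is not counted as having completed the study. The clause on Study 661-110 shows that the authors meant to count subjects who correctly have no Safety Follow-up Visit. The parallel case looks like an omission.

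In the by-visit safety tables, two subjects with readings on the same study day, equally long off drug, are shown under different visit labels solely because of what the visit was called. All those affected stopped drug early, and in small groups one subject is visible in the percentages.

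**Working it through.** The plan gives no figure to reproduce. The check applies its rules to a subject whose ETT Visit replaces Safety Follow-up.

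**1. Disposition.** An ETT Visit exists only for early stoppers: "If a subject prematurely discontinues treatment, an Early Termination of Treatment (ETT) Visit should be scheduled as soon as possible". The route through completing all study drugs is therefore closed. The route through a completed Safety Follow-up Visit is closed on the SAP's own wording, because 8.1 lists these subjects among those without one. Neither route is met, however late the ETT Visit is.

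**2. Size in the disposition table.** Percentages are based on the Full Analysis Set, so one subject moves the completion rate by 100/n points. Planned group sizes follow from the randomization ratios.

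| Group | Planned n | Shift per subject |
|---|---|---|
| TC-1A | 10 × 4/5 = 8 | 12.5 points |
| TC-1B-low | 32 × 1/4 = 8 | 12.5 points |
| TC-1B-high | 32 × 2/4 = 16 | 6.3 points |
| TC-2 | 24 × 3/4 = 18 | 5.6 points |
| TEZ/IVA (Part 2) | 24 × 1/4 = 6 | 16.7 points |

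**3. Which by-visit readings are affected.** SAP 8.4 restricts safety analyses to TE-period data, and with no Safety Follow-up Visit that period ends 28 days after the last dose. Replacement requires at least 21 days. The gap g between last dose and ETT Visit therefore runs from 21 to 28 days for this part of the point.

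**4. Where they land.** For last dose on Day L, the ETT Visit is on Day L + g. The Table 11-5 windows for chemistry, hematology, urinalysis and vital signs are Day 29 = (22, 36], Day 43 = (36, 50] and, in Part 2, Day 57 = (50, 71]. The Day 15 window ends at Day 22. The planned last dose is Day 29 in Part 1 and Day 57 (TEZ/IVA) in Part 2, so early stops are L = 1 to 28 and L = 1 to 56.

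| Part, gap | Day 15 | Day 29 | Day 43 | Day 57 | No window |
|---|---|---|---|---|---|
| Part 1, g = 21 | L = 1 | L = 2–15 | L = 16–28 | – | – |
| Part 1, g = 28 | – | L = 1–8 | L = 9–22 | – | L = 23–28 |
| Part 2, g = 21 | L = 1 | L = 2–15 | L = 16–29 | L = 30–50 | L = 51–56 |
| Part 2, g = 28 | – | L = 1–8 | L = 9–22 | L = 23–43 | L = 44–56 |

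No combination reaches the Safety Follow-up row. Urinalysis is windowed but only listed under SAP 8.4.2, so it changes no summary. Coagulation is not collected at the ETT Visit. The ECG is collected there but has no by-visit row for any L.

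**5. Two records side by side.** Both subjects take the last dose on Day 8.

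- Subject A has the ETT Visit on Day 10 and Safety Follow-up on Day 30 (30 − 8 = 22 days, inside 28 ± 7). A is a completer, and the Day 30 readings are shown as Safety Follow-up.
- Subject B has only an ETT Visit, on Day 30, also 22 days after the last dose, and it replaces Safety Follow-up. B is not a completer. The Day 30 chemistry is shown as Day 29, assuming no other reading in that window is preferred. The ECG has no by-visit row.

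**The case against.** **The SAP does recognise the case.** A reader might infer that it identifies Safety Follow-up by visit name alone. It does not: SAP 8.1 names the replacing ETT Visit for Part 2, and the 28-day rule covers it in Part 1. The gap is limited to 8.2.1 and Table 11-5.

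**Readings are not simply moved to Day 29 or lost.** A reader might infer this too. Depending on the stop day they can fall under Day 15, 43 or 57 as well, and readings more than 28 days after the last dose are outside the TE summaries anyway. Listings keep everything. Threshold summaries, maximum-value liver plots and lowest-oxygen-saturation shifts run over the TE period, not by visit label. Early stopping has its own disposition line, and adverse events leading to discontinuation are tabulated separately.

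**Windowing by study day is the stated method.** SAP 8.3 deliberately keeps efficacy measurements taken after treatment discontinuation, so an off-drug efficacy reading in the Day 29 window is not an error.

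**Misclassification is partly inferred.** Nothing states that such a subject goes under premature study discontinuation, which calls for a reason that this subject may not have. A programmer could treat the replacing ETT Visit as Safety Follow-up, and the case report form and internal programming rules are not available to check. This stands as a limit on the claim. It does not close the gap, because the SAP's wording in 8.1 points the other way.

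**The case should be rare**, since the ETT Visit is to be held as soon as possible. That stands.

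**Conclusion.** The point holds and is minor. As written, SAP 8.2.1 leaves a protocol-compliant subject out of the completion count, and Table 11-5 gives that subject's last visit no Safety Follow-up row and its ECG no by-visit row.

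The disposition effect applies to any replacing ETT Visit and is 1/n per subject, from 5.6 points (n = 18) to 16.7 points (n = 6) in the groups tabulated. This is arithmetic for one hypothetical subject; the documents do not say how many there will be. The by-visit effect applies only to gaps of about 21 to 28 days.

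The conclusion assumes a literal reading of 8.2.1, planned group sizes, and the SAP's own classification of these subjects as having no Safety Follow-up Visit. The documents do not support any effect on efficacy estimates or tests, or any loss of safety data.

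**What to change.** 1. **SAP 8.2.1:** extend the completion definition with *or attended an ETT Visit at least 3 weeks after the last dose that took the place of Safety Follow-up under protocol 8.1.6*.
2. **SAP Table 11-5:** state that safety readings from such an ETT Visit, including the ECG, are assigned to the Safety Follow-up row when they fall within the TE period, instead of to a study-day window.
3. **SAP 8.1:** align the wording that these subjects have no Safety Follow-up Visit, for example by referring to no *separate* visit, and keep the 28-day end of the TE period. Without this, the second change would contradict 8.1.
4. Leave efficacy windowing as it is.

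The cost is three short SAP edits and one derived flag (ETT date minus last dose date of at least 21 days). Study conduct does not change. The one downside is a slightly smaller n in the study-day windows that those readings leave.

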## 8.2.2 Demographics and Baseline Characteristics

Demographics, medical history and baseline characteristics will be summarized based on the FAS, and presented by treatment group and overall, for each part and cohort, as applicable.

Demographic data will include the following:

- Age at baseline (in years)
- Sex (female and male)
- Ethnicity (Hispanic or Latino, not Hispanic or Latino, and not collected per local regulations)
- Race (White, Black or African American, Asian, American Indian or Alaska Native, Native Hawaiian or Other Pacific Islander, and Other)

Baseline characteristics will include the following:

- Weight (kg)
- Height (cm)
- BMI (kg/m^2)

Stratification categories will include the following:

- ppFEV1 at stratification (< 70 and ≥ 70)

For subjects who are naïve to TEZ/IVA treatment in Part 2, ppFEV1 at Day -14 will be used for stratification; otherwise, ppFEV1 at screening will be used for stratification.

Disease characteristics will include the following:

- ppFEV1 at baseline (<40, ≥ 40 to <70, ≥70 to ≤90, >90)
- ppFEV1 at baseline (continuous)
- Sweat Chloride at baseline (continuous)
- FEV1 (L) at baseline (continuous)
- CFQ-R Respiratory Symptoms domain at baseline (continuous)
- Prior use of dornase alfa before first dose of study drug (Yes, No)
- Prior use of inhaled antibiotic before first dose of study drug (Yes, No)
- Prior use of any bronchodilator before first dose of study drug (Yes, No)
- Prior use of any inhaled bronchodilator before first dose of study drug (Yes, No)
- Prior use of any inhaled hypertonic saline before first dose of study drug (Yes, No)
- Prior use of any inhaled corticosteroids before first dose of study drug (Yes, No)

- Colonization with *Pseudomonas aeruginosa* at baseline (Positive, Negative)

A summary of medical history will be provided by MedDRA system organ class (SOC) and preferred term (PT) for the FAS. In addition, the number of subjects reported to have had positive cultures for respiratory pathogens in 2 years prior to screening will be summarized for the FAS. Further, the CFTR genotype for each subject will be provided in an individual subject data listing.

